In addition, prostate-specific membrane antigen (PSMA) recently has received increased attention (27). This cell surface protein is significantly overexpressed in prostate cancer cells when compared to other PSMA-expressing tissues such as kidney, proximal small intestine or salivary glands (28). It therefore provides a promising target for prostate cancer-specific imaging (29). Recently methods have been developed to label PSMA ligands with ^{68}Ga enabling their use for PET imaging and therapy (30). Initial experience with PET/CT using Glu-NH-CO-NH-Lys-(Ahx)-[^{68}Ga (HBED-CC)] (^{68}Ga -PSMA-11) as a ^{68}Ga -labelled PSMA ligand suggests that this novel tracer can detect prostate cancer relapses and metastases with high contrast by binding to the extracellular domain of PSMA, followed by internalization (31). Improved detection of occult metastatic disease will improve treatment efficacy by enabling better patient selection for treatment and prompting more extended pelvic node treatment with surgery or radiation for patients with evidence of nodal metastases outside the normal lymph node treatment area.

We conducted a pilot phase evaluation of ^{68}Ga -PSMA-11 under an RDRC-approved protocol at Stanford University. Ten men (age range: 67 to 83 year-old; mean \pm SD: 73.1 ± 5.7) with biochemical recurrence of prostate cancer (PSA range: 2.6-36.4; mean \pm SD: 12.4 ± 10.6) were enrolled. PET/CT images were acquired at 51 to 68 minutes (mean \pm SD: 57.4 ± 6.3) after injection of 3.7 to 4.0 mCi (mean \pm SD: 3.8 ± 0.1) of ^{68}Ga -PSMA. The uptake of ^{68}Ga -PSMA-11 was identified as described in previously published studies referenced above.

All participants had multiple standard of care imaging studies (CT, MRI, ^{18}F -FDG PET/CT, ^{18}F -NaF PET/CT, $^{99\text{m}}\text{Tc}$ MDP bone scan) prior to enrollment that were non-contributory, despite rising PSA values. The participants did not receive treatment in this interval as they were managed under a wait and watch strategy due to no identifiable disease. The interval

from biochemical recurrence to the ^{68}Ga -PSMA-11 PET/CT scan ranged 5 to 75 months (mean \pm SD: 30.8 ± 20.4).

Biodistribution and localization of ^{68}Ga -PSMA-11

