2.5 Study Design

This is a phase 2-3 study with a total of 200 participants with newly-diagnosed intermediate or high-risk prostate cancer scheduled to undergo prostatectomy and lymph node dissection. Eligible participants will undergo baseline assessments at enrollment. Study participants will receive ^{68}Ga -PSMA-11 and undergo a PET/MRI. All patients will first be seen by a Stanford Cancer Institute physician (Drs [name], [name], [name] and [name]) who will refer patients if appropriate on clinical grounds to Dr [name] or his colleagues for this study. The following steps will take place.

1. After signed the informed consent document, participants will be given a copy of the signed form.
2. Participant will be asked to drink 1 to 2 glasses of water before arrival at the clinic
3. Participants will be weighed and vital signs (heart rate and blood pressure) will be recorded
4. Study personnel (eg, technologist) will verify subject identify; radiopharmaceutical identity; dose; and administration route. Participant will be injected IV with 3 to 7 mCi of ^{68}Ga -PSMA-11
5. Participant will void immediately prior to the scan

6. Approximately 50 to 100 minutes after the radiopharmaceutical IV administration, data acquisition will begin in the pelvic region and move toward the head. First, localizer MRI scans will be performed to define the table positions. After correct positioning of the spatial acquisition windows is ensured, the combined PET/MRI acquisition will be initiated with 3 to 5 table positions at a 4-min acquisition time per table position.
7. Vital signs (heart rate and blood pressure) will be recorded again at the completion of the study.
8. Participants will be dismissed.
9. Participants will be contacted at 24 to 72 hours following the scan in order to capture potential late occurring Adverse Events.

The ^{68}Ga -PSMA-11 PET/MRI may be repeated at the completion of treatment to evaluate response to therapy, if requested by the treating physician.

Objectives of the Study

Primary

- Sensitivity, specificity, positive and negative predictive value of ^{68}Ga -PSMA-11 PET/MRI for the detection of regional nodal metastases compared to pathology at radical prostatectomy on a per patient basis using nodal regional correlation.

Secondary

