3. PARTICIPANT SELECTION AND ENROLLMENT PROCEDURES

3.1 Inclusion Criteria

- ≥ 18 years-old
- Biopsy-proven prostate adenocarcinoma
- Planned prostatectomy with lymph node dissection
- Intermediate to high-risk disease (as determined by elevated PSA [$PSA > 10$], T-stage [$T2b$ or greater], Gleason score [Gleason score > 6] or other risk factors)
- Able to provide written consent.
- Karnofsky performance status of ≥ 50 (or ECOG/WHO equivalent)
- Diagnostic CT or MRI performed within 90 days of the research PET

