10.2 Determination of Sample Size and Accrual Rate

10.2.1 Sample Size and Power Estimate

The estimated sample size will be 200 patients to adequately power the primary aim. The power analysis will be based on the comparison of sensitivity between conventional imaging and PSMA-11 PET. With a power of 80% and a significance level of 0.01, a sample size of 61 patients with nodal metastases is required. The following assumptions are made:

- i. 30% of intermediate to high-risk patients have nodal metastases at prostatectomy.

- ii. 25% of patients will not undergo the planned prostatectomy. Patients that do not undergo prostatectomy will not be included in the analysis population, and will not undergo central imaging review.
- iii. Conventional imaging has a 45% detection sensitivity for nodal metastases on a per-patient basis (2).
- iv. PSMA-11 PET has a 65% detection sensitivity for nodal metastases on a per-patient basis.

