10.3.4 Analysis of Exploratory Endpoints

PPVs on a per-patient and per-region-basis of ^{68}Ga -PSMA-11 PET for detection of tumor location confirmed by histopathology/biopsy and conventional imaging follow-up will be calculated and reported along with the corresponding two-sided 95% confidence intervals. The paired McNemar's test will be used to compare the PPVs of ^{68}Ga -PSMA-11 PET imaging to the PPVs of conventional imaging.

Sensitivity, specificity, and NPVs on a per-patient basis of ^{68}Ga -PSMA-11 PET for detection of tumor location confirmed by histopathology/biopsy will be summarized in tabular format. Furthermore, the positive and negative likelihood ratios (LR+ and LR-) will be calculated and reported. 95 confidence intervals of sensitivity, specificity, and NPV will be calculated using the Wilson score method. The comparisons of sensitivity, specificity, and NPV on a per-patient basis of ^{68}Ga -PSMA-11 PET imaging will be compared to of sensitivity, specificity, and NPV on a per-patient basis of conventional imaging using a paired McNemar's test.

Detection rates on a per-patient basis of ^{68}Ga -PSMA-11 PET stratified by PSA value (0.2 to < 0.5; 0.5 to < 1.0; 1.0 to < 2.0; 2.0 to < 5.0; ≥ 5.0) will be summarized in tabular format and compared between PSA strata using chi-square analysis. The impact of ^{68}Ga -PSMA-11 PET on clinical management in BCR patients will be evaluated using descriptive statistics.

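### The comparison of PET detection across PSA bands in 10.3.4 has little power in newly diagnosed men, mainly because of where the bands lie and partly because the chi-square ignores their order

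*Combined protocol and SAP*

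**What the plan says.** The analysis is in the section headed "10.3.4 Analysis of Exploratory Endpoints" of the combined protocol and SAP. Per-patient detection rates are to be "stratified by PSA value (0.2 to < 0.5; 0.5 to < 1.0; 1.0 to < 2.0; 2.0 to < 5.0; ≥ 5.0"), and these rates "will be summarized in tabular format and compared between PSA strata using chi-square analysis". The section names no trend test, no model with PSA as a continuous variable, no significance level and no expected effect. It gives no reason for the cut-points.

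The next sentence says that the impact of PET "on clinical management in BCR patients will be evaluated using descriptive statistics". BCR stands for biochemical recurrence. Section 2.5, however, describes "200 participants with newly-diagnosed intermediate or high-risk prostate cancer scheduled to undergo prostatectomy and lymph node dissection". Under section 3.1, a PSA above 10 is one of several routes into the trial ("Intermediate to high-risk disease (as determined by elevated PSA" is followed by T-stage, Gleason score and other risk factors). The documents give no PSA distribution for this population.

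**The concern.** PSA is continuous, and the natural question is whether detection rises with it. A between-group chi-square on five ordered bands gives the same answer if the bands are shuffled, and it spends up to 4 degrees of freedom on what is mainly a one-directional question. The bands also separate low PSA values finely and put everything from 5.0 upward together. That may suit recurrence after treatment. Before prostatectomy it leaves most patients in one cell.

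This is the plan's only test of detection against PSA, and the background treats performance at low PSA as a selling point of the tracer (sections 2.1 and 2.4). If power is low, a non-significant p-value could be read as showing that detection does not depend on PSA. A p-value without an effect estimate would not correct that impression.

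**Working it through.** **Plan's own figure.** There is none to reproduce. The only sizing statement, in 10.2.1 ("The estimated sample size will be 200 patients to adequately power the primary aim"), concerns the sensitivity comparison.

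**Inputs from the documents**
- Patients: 200 × (1 − 0.25) = 150 operated (10.2.1). The same section excludes unoperated patients from central image review, so 150 is the natural denominator.
- PET positivity: prevalence × sensitivity + (1 − prevalence) × (1 − specificity) = 0.30 × 0.65 + 0.70 × 0.10 = 0.265. Prevalence and sensitivity are from 10.2.1; the 90% specificity is the success threshold in 10.3.2.

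**Assumptions, not in the documents**
- Log-normal PSA, median 7 to 10, log SD 0.7.
- Log-linear logistic relation, with an odds ratio (OR) per doubling of 1.3 to 2.0.
- Two-sided 0.05.

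**Step 1: where patients fall.** The share at ≥5.0 is Φ(ln(median/5)/0.7).
- Median 7: Φ(0.481) = 0.68, about 103 of 150.
- Median 10: Φ(0.990) = 0.84, about 126 of 150.

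The share below 2.0 is Φ(ln(2/median)/0.7).
- Median 7: Φ(−1.790) = 0.037, about 5.5 of 150.
- Median 10: Φ(−2.299) = 0.011, about 1.6 of 150.

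The three lowest bands together therefore hold about 2 to 6 patients, with 0.4 to 1.5 expected detections (1.6 × 0.265 and 5.5 × 0.265). Even the pilot's recurrence patients in section 2.1, with PSA from 2.6 to 36.4, would have used only the top two bands.

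**Step 2: power of the comparison.** Simulation with 2,000 to 4,000 trials per setting, so the simulation standard error is at most √(0.25/2000) = 1.1 points. N = 150; ranges cover median 7 to 10.

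| OR per doubling | Chi-square, plan's bands | Chi-square, quintiles | Trend test, quintiles | 1-df test, log PSA |
|---|---|---|---|---|
| 1.3 | 7-10% | 16-17% | 26-27% | 29-30% |
| 1.5 | 12-20% | 32-34% | 53-54% | 56-58% |
| 1.7 | 21-31% | 53-55% | 74-76% | 78-81% |
| 2.0 | 32-52% | 77% | 92% | 94-95% |

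Type I error was 4-6% for every test. The sparse cells therefore cost power here and did not inflate false positives. N = 200 gave the same pattern.

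**Step 3: how much is order and how much is placement (OR 1.5).** A trend test on the plan's own bands reaches 21% (median 10) to 36% (median 7).
- Median 10: restoring order gains 21 − 12 = 9 points; the gap left to log PSA is 56 − 21 = 35.
- Median 7: restoring order gains 36 − 20 = 16 points; the gap left is 58 − 36 = 22.

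The remaining 22 to 35 points come from the banding. Most of that is placement, because a trend test on quintiles comes within about 5 points of log PSA.

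**Step 4: the cost of order in general.** With equal-sized bands and a linear relation, both tests have the same noncentrality.
- 80% power with 1 df (noncentrality 7.85) becomes 59.5% with 4 df.
- Regaining 80% with 4 df needs noncentrality 11.94, that is 11.94/7.85 = 1.52 times the patients.
- The largest relative loss at any effect size is 41% (30.3% to 17.7%).

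**The case against.** **The size rests on assumptions.** This stands. Neither the PSA distribution nor the odds ratio comes from the documents. A broader distribution reaching into the low bands would shrink the loss. With an assumed median of 1.2 and log SD of 1.2, at OR 1.3 and N = 150, the chi-square reaches 49% against 78% for continuous log PSA. Entry requires intermediate to high-risk disease, so that distribution is unlikely here.

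**The test may not be unordered.** The section says only chi-square analysis, which could cover a chi-square for trend. Comparing between strata reads most naturally as the unordered test, and the section names its other methods specifically (Wilson score, paired McNemar). A trend test on these bands would still reach only 21-36% at OR 1.5, so this objection narrows the point without removing it.

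**Ignoring order is not what loses most of the power.** A reader might infer that it is, and that the choice of test can be judged apart from the cut-points. The figures do not support either inference. Order alone costs 9 to 16 points on the plan's bands at OR 1.5, and at most 41% of power with five equal bands. An unordered chi-square on better-placed bands still reaches 32-34% (quintiles) or 38-40% (<10, 10-20, >20). The split does depend on the bands: on quintiles, ignoring order costs about 20 points (53-54% against 32-34%).

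**Low stakes.** This also stands. Detection by PSA is not among the exploratory objectives or endpoints listed in the synopsis and section 2.5. No power claim attaches to it, and the success rule in 10.3.2 does not use it.

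**Conclusion.** The point holds as a minor improvement to an exploratory analysis. Under the stated assumptions the planned comparison has 12-20% power at OR 1.5 and 32-52% at OR 2.0, against 56-58% and 94-95% for a 1-df test on log PSA. On the plan's own bands, most of the shortfall comes from cut-points that place roughly 68-84% of newly diagnosed men in the top band; the smaller part comes from ignoring order.

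Two further inferences should not be drawn. One is that any real relation would probably be missed: at OR 2.0 with median 7, the planned test is significant about half the time, while at OR 1.3 the log-PSA test itself has only about 30% power. The other is that the trial's main conclusion is at risk; nothing in the primary analysis depends on this comparison.

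**What to change.** In 10.3.4, keep a table of detection rates by PSA band as description and replace the chi-square comparison with wording such as:

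> *The relation between PSA and PET positivity will be estimated by logistic regression of per-patient positivity on log2 of baseline PSA, reported as the odds ratio per doubling with its 95% confidence interval.*

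If a banded test is also wanted, use a Cochran-Armitage trend test on bands that fit this population, such as quintiles. Putting it on the existing bands would recover little. State the denominator (200 scanned or about 150 operated) and which read counts as positive, and reconcile the bands and the BCR sentence with the enrolled population.

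The cost is a sentence or two. The regression assumes a roughly log-linear relation, which the retained table lets readers check. It needs a baseline PSA for every patient. Eligibility does not guarantee one, because PSA is only one of several risk criteria, and the study calendar has no PSA entry. The table already planned needs the same value, so the change adds no new data requirement.

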3.2 Exclusion Criteria

- Patients not capable of getting PET study due to weight, claustrophobia, or inability to lay still for the duration of the exam
- Neoadjuvant chemotherapy or radiation therapy prior to prostatectomy, including focal ablation techniques (HiFu)
- Androgen deprivation therapy or other neoadjuvant treatments prior to PET imaging and surgery
- Metallic implants (contraindicated for MRI)

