10.4 Accrual estimates

We expect the accrual of 40 patients each year for 5 years. There are approximately 120 radical prostatectomies performed on patients with newly diagnosed prostate cancer at Stanford each year. We plan to enroll 40 participants/year and this is achievable given our experience with other protocols and the support from the referring physicians, Drs [name], [name], [name], and [name].

Inclusion/Exclusion Criteria Checklist

Protocol Title:	68Ga-PSMA-11 PET/MRI for detection of regional nodal and distant metastases in patients with intermediate and high-risk prostate cancer		
Protocol Number:	IRB-35931 / PROS0075		
Principal Investigator:	[name]		

Inclusion Criteria – Yes must be checked to be eligible (From IRB approved protocol)	Yes	No	Supporting Documentation
1. ≥ 18 years-old			
2. Biopsy-proven prostate adenocarcinoma			
3. Planned prostatectomy with lymph node dissection			
4. Intermediate to high-risk disease (as determined by elevated PSA [PSA>10], T-stage [T2b or greater], Gleason score [Gleason score > 6] or other risk factors)			
5. Able to provide written consent			
6. Karnofsky performance status of ≥ 50 (or ECOG/WHO equivalent)			
7. Diagnostic CT or MRI performed within 90 days of the research PET			

Exclusion Criteria –No must be checked to be eligible (From IRB approved protocol)	Yes	No	Supporting Documentation
1. Patients not capable of getting PET study due to weight, claustrophobia, or inability to lay still for the duration of the exam			
2. Neoadjuvant chemotherapy or radiation therapy prior to prostatectomy including focal ablation techniques (HiFu)			
3. Androgen deprivation therapy or other neoadjuvant treatments prior to PET imaging surgery			

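### Two exploratory analyses in section 10.3.4 are written for a recurrence population: the biochemical-recurrence analysis has no eligible patients at the study scan, and the PSA strata pool every man who enters on PSA above 10

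*Combined protocol and SAP*

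**What the plan says.** Section 10.3.4 (Analysis of Exploratory Endpoints) ends with two analyses.

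- Per-patient detection rates are "stratified by PSA value (0.2 to < 0.5; 0.5 to < 1.0; 1.0 to < 2.0", followed by 2.0 to below 5.0 and then 5.0 and above. They are to be tabulated and compared between strata by chi-square.
- The impact of the study "PET on clinical management in BCR patients will be evaluated using descriptive statistics".

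The population is set elsewhere.

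- Section 2.5 (Study Design) enrols "200 participants with newly-diagnosed intermediate or high-risk prostate cancer scheduled to undergo prostatectomy and lymph node dissection".
- Section 3.1 requires "Planned prostatectomy with lymph node dissection".
- The risk criterion, in section 3.1 and again in the eligibility checklist, is "Intermediate to high-risk disease (as determined by elevated PSA [PSA>10], T-stage [T2b or greater], Gleason score [Gleason score > 6] or other risk factors".
- Section 3.2 excludes "Neoadjuvant chemotherapy or radiation therapy prior to prostatectomy, including focal ablation techniques (HiFu", and also androgen deprivation before imaging and surgery.

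**The concern.** Strata starting at 0.2 and an analysis confined to men with biochemical recurrence suit a study of men whose PSA is rising after treatment. This trial images men who still have the prostate in place.

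Two things are at stake. One stated analysis has nobody to analyse at the study scan. The other spends four of its five strata on PSA values below 5 and leaves the range that bears on eligibility undivided, so it cannot show whether detection differs on either side of 10. If the text stays as it is, replacement cut-points or a replacement population would have to be chosen once data are in hand.

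**Working it through.** The plan states no count or power for either analysis, so there is no figure to reproduce. The check has two parts.

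**1. Who can be in the recurrence analysis?**

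- Entry: sections 2.5 and 3.1 require a new diagnosis and a planned prostatectomy. Section 3.2 excludes men who have had radiation or focal ablation first. No criterion admits biochemical recurrence. Eligible at the study scan: 0 of 200.
- Later scans: the study calendar (section 7) has one scan date. Repeat PSMA PET is optional in section 2.5 (response after treatment), section 5.3 (a PET-positive node not confirmed by pathology) and section 10.3.3 (a negative biopsy). None is tied to recurrence.
- Context: BCR is not in the list of abbreviations, and the only recurrence cohort described is the ten-man pilot in section 2.1. Neither analysis appears among the exploratory objectives or endpoints in the synopsis or section 2.5.

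**2. How full are the PSA strata?**

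The strata carry no unit; ng/mL is assumed. Every man who enters on PSA above 10 falls in the stratum of 5.0 and above. Men may also enter on T-stage, Gleason score or other factors, and there is no PSA floor, so values below 5 are possible.

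Inputs:

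- N = 200 enrolled, or 200 × (1 − 0.25) = 150 operated (section 10.2.1).
- Share f with PSA below 5: not in the documents; assumed 2% to 30%.
- Detection rate r: assumed 20% or 30%. As a guide, the plan's 30% nodal prevalence and 65% sensitivity (section 10.2.1) with its 90% specificity threshold (section 10.3.2) give 0.30 × 0.65 + 0.70 × 0.10 = 0.265 positive for pelvic nodes.
- Spread of the f × N men over the four lower strata: equal, or in proportion to stratum width (0.3, 0.5, 1.0, 3.0; total 4.8).

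The table is 5 strata × 2 outcomes, or 10 cells. Expected counts in a stratum of n men are n × r and n × (1 − r).

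Worked case, N = 200, f = 10%, r = 30%: 20 men lie below 5.

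- Equal spread: 5 per stratum; expected 1.5 detected and 3.5 not detected. All 8 lower cells are below 5.
- Width-proportional spread: 1.25, 2.08, 4.17 and 12.5 men. Detected 0.38, 0.63, 1.25 and 3.75; not detected 0.88, 1.46, 2.92 and 8.75. Seven cells are below 5.
- Top stratum: 180 men, expected 54 and 126.

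Cells with expected count below 5, out of 10, over both detection rates and both spreads:

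| Share with PSA below 5 | Men below 5, N = 200 | Cells, N = 200 | Men below 5, N = 150 | Cells, N = 150 |
|---|---|---|---|---|
| 2% | 4 | 8 | 3 | 8 |
| 5% | 10 | 7 to 8 | 7.5 | 8 |
| 10% | 20 | 7 to 8 | 15 | 7 to 8 |
| 20% | 40 | 4 to 5 | 30 | 4 to 6 |
| 30% | 60 | 4 to 5 | 45 | 4 to 5 |

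Men needed below 5, evenly spread, for every expected count to reach 5: 4 × 5 / r.

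- r = 30%: 4 × 16.7 = about 67 men (33% of 200, 44% of 150).
- r = 20%: 4 × 25 = 100 men (50% of 200, 67% of 150).
- r = 50%: 4 × 10 = 40 men (20% of 200, 27% of 150).

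**The case against.** The best reply is that this is leftover wording in an exploratory paragraph. No objective asks how detection varies with PSA, and no success criterion or sample-size input uses either analysis. That stands, and it sets the severity.

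A second reply is that sparse cells upset only the chi-square approximation. An exact test would deal with that, and the tabulated detection rates remain usable. That stands for the test. It does not help with the undivided top stratum, which is a fault of the cut-points whatever test is used.

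A third reply is that men may progress after surgery, since one-year PSA progression-free survival is an exploratory objective, and could then have a repeat PET. This is possible, but the plan schedules no such scan and does not say that these are the patients meant.

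Three stronger readings are tempting and are not supported:

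- That the lower strata will be nearly empty. The documents give no PSA distribution, and PSA above 10 is only one entry route. With 30% of 200 men below 5, the 2.0 to below 5.0 stratum alone could hold 60 × 3.0 / 4.8 = 37.5 men.
- That there can be no recurrence patients at any time. The documents support none at the study scan.
- That 20 ng/mL is already a trial cut-off. It appears only in the background (section 2.1), in describing guideline staging.

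**Conclusion.** The mismatch is real and minor. Two parts need no assumption: no man with biochemical recurrence is eligible at the study scan, and every man qualifying on PSA above 10 falls in one stratum.

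The sparseness is likely rather than certain. It rests on an assumed 2% to 30% of men with PSA below 5 and detection of 20% to 30%, over which 4 to 8 of 10 cells have expected counts below 5. It would ease if more men had low PSA or detection were higher: at 50% detection, 40 evenly spread men would be enough.

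A reader might go on to infer that the trial's main result is at risk. It is not: both analyses are exploratory, and neither feeds the primary endpoint, the success rule or the sample size.

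**What to change.** 1. Name baseline PSA, measured before the scan, as a recorded analysis variable. The study calendar does not list it, and a man need not qualify on PSA.
2. Replace the five strata with cut-points suited to PSA before prostatectomy, including the eligibility value of 10. A further cut such as 20 is optional.
3. Replace the five-stratum chi-square with an exact or trend test, or model detection on PSA as a continuous variable.
4. Delete the recurrence-patient analysis, or redefine it for enrolled patients. Redefinition works only if planned management before and after PET is recorded, which the calendar does not now provide.
5. List whatever is kept among the exploratory objectives and endpoints. Reconcile section 10.3.3 as well, where the negative-biopsy rules speak of suspected recurrence.

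Cost: deletion and re-cutting are changes of text. Recording baseline PSA adds one data item, and a redefined management analysis adds a record before and after the scan. No scan and no change of sample size is needed.
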